Student researcher [name], BS, is medical student at the University of Miami. He will assist in subject recruitment, and study procedures, and data entry.

All study personnel will complete their CITI training and be adequately informed about the protocol and study procedures. All duties and functions are appointed and overseen by the PI.

20) **Prior Approvals**

Approved under FDA IND 134066.

21) **Recruitment Methods**

IRB approved flyers will be placed around the University of Miami medical campus, and within the waiting rooms of the Department of Dermatology Out Patient Clinic at UMH (South Building, suites K-M) and at the Lennar Foundation Medical Center.

Subjects are compensated \$25 at the completion of each study visit for a total of \$50 for 2 visits.

22) **Confidentiality**

We will not be accessing or adding to any medical records. Information will be collected directly from the subject, and will be used for research purposes only. Every attempt will be made to ensure any information gathered is kept secure. All study data will be kept in a locked office and kept under password protection on a computer that is only accessible by study personnel.

23) **Provisions to Protect the Privacy Interests of Subjects**

Study subjects will only be asked to provide personal information to approved study personnel, who will ensure the subject is at ease with the situation. Study personnel will clearly explain that the subject does not have to answer any questions or provide any sample they are uncomfortable about.

24) **Compensation for Research-Related Injury**

Treatment will be available if enrolled subjects get sick or injured. However, the subject or the subject's insurance will be responsible for these costs. Funds to compensate for pain, expenses, lost wages, and other damages caused by injury are not available.

25) **Economic Burden to Subjects**

There will be no charges to the subjects that agree in participating in this study.

26) **Consent Process**

The research team will follow the "HRP-090 SOP: Informed Consent Process for Research" to obtain informed consent and the "HRP-091 SOP: Written Documentation of Informed Consent" to document informed consent in writing.

Study personnel will meet with each potential subject to discuss the study in detail, answer questions, and allow the subject to read the entire consent form. The informed consent form explicitly states the rationale for the study and requirements for participation, both before and during the session. The informed consent form states that subjects may discontinue participation or be terminated from the study at any time.

All pertinent aspects of the study will be explained to the subject before he or she signs the informed consent form. A signed informed consent form will be obtained from the subject before any activity or treatment is undertaken as part of the study.

Non-English Speaking Subjects will not be enrolled. Our current research team does not have a member that fluently speaks Spanish. We are actively trying to recruit such a member and will submit translated consent forms once we hire such personnel. Subjects who are not yet adults (infants, children, teenagers), cognitively impaired adults, and adults unable to consent will not be enrolled.

27) **Process to Document Consent in Writing**

The research team will follow the “HRP--091 SOP: Written Documentation of Informed Consent” to document informed consent in writing.

28) **Drugs**

Cowhage:

Cowhage (*Mucuna pruriens*) is a tropical legume also known as Velvet bean or cowitch and it is found in Latin America, the Caribbean, India, Africa and Florida. *M. pruriens* is a climbing vine and considered variously as an annual or perennial. The plant consists of a vine with slender stems that bear numerous alternate, trifoliolate leaves approximately 10cm long. The flowers are typically purple, red or green-yellow. The fruit pods range from 3-10 cm in length, are curved and, when mature, are covered with dark hairs/spicules that provide a velvety appearance. The pods contain 4-6 seeds that are approximately 1 x 1 cm.

The dry pods are collected by cutting the stems from the plant and letting them fall directly into a clean, dry polythene bag. The spicules are separated from the pods by shaking the bag. Forceps are used to remove the pods and retain the spicules. The cowhage spicules are shipped at room temperature since they are stable unless exposed to extreme heat and pressure via autoclaving (>100°C), which renders them chemically inert.

Once it reaches the lab, [name] staff documents on the tube the date of arrival. This batch is labeled the “master batch”. The tube of cowhage is then stored under dry conditions in a 4°C refrigerator. Also

upon arrival, the spicules are examined under a microscope to confirm the material is cowhage. The dimensions of the spicules (2-4 mm length, 1-3 µm tip diameter) are measured⁴⁰.

The investigator then tests the spicules for the itch induction ability with the same application method used in studies⁵⁷. Forty to forty-five spicules (a dose found to induce a consistent and reproducible itch sensation) are counted under the microscope and then rubbed in to a 4x4 cm area on the volar forearm for 45 seconds in a circular motion. Approximately 0.2 mm of the spicule tip enters the skin. Forty-five spicules of cowhage are equivalent to 45 µg of material, containing about 90-140 ng of mucunain⁴⁵. The spicules usually induce itch after ~30-90 seconds of the application. If 2 minutes pass without itch being induced, the spicules are deemed inactive and the batch will not be used for itch induction in studies. If itch is induced, the itch sensation will last ~7 minutes and itch intensity is rated using a 0-10 numerical rating scale (NRS) every 30 seconds until the itching subsides. Cowhage spicules are removed from the skin using tape, which is disposed of in a biohazard trash bin. The itch subsides quickly once the spicules have been removed. Itch is only felt at the site of induction and mild temporary erythema at the induction site is common.

For studies using cowhage to induce itch, a small portion of the master batch of cowhage is aliquoted into smaller 5 ml tubes as a “working batch”. The date of separation from the main batch is marked on the smaller tube. This tube then remains at room temperature for the duration of the study. The potency of the cowhage is preserved for many years when stored in a dehumidified area at room temperature or at 4°C, but the potency is checked every 3 months and before the start of any study.

Drug Formula for Ketamine 10% - Amitriptyline 5% - Lidocaine 5% (Per 100gm of cream)

- Ketamine HCl (Fagron Pharmaceuticals NDC 51552-0697-07): 10grams
- Amitriptyline HCl (Medisca NDC 38779-0189-09): 5 grams
- Lidocaine HCl (Medisca NDC 38779-0082-03): 5 grams
- Ethoxy Diglycol (Fagron Pharmaceuticals NDC 38779-1903-07): 5mL
- Liquigel (Medisca NDC 38779-2531-01): 3 grams
- Lipoderm Cream Base (PCCA NDC 51927-3338-00): 72 grams

Drug Formula for Ketamine 10% (Per 100gm of cream)

- Ketamine HCl (Fagron Pharmaceuticals NDC 51552-0697-07): 10grams
- Ethoxy Diglycol (Fagron Pharmaceuticals NDC 38779-1903-07): 4mL
- Liquigel (Medisca NDC 38779-2531-01): 3 grams
- Lipoderm Cream Base (PCCA NDC 51927-3338-00): 83 grams

Drug Formula for Amitriptyline 5% (Per 100gm of cream)

- Amitriptyline HCl (Medisca NDC 38779-0189-09): 5 grams
- Ethoxy Diglycol (Fagron Pharmaceuticals NDC 38779-1903-07): 3mL
- Liquigel (Medisca NDC 38779-2531-01): 3 grams
- Lipoderm Cream Base (PCCA NDC 51927-3338-00): 89 grams

Drug Formula For Lidocaine 5% (Per 100gm of cream)

- Lidocaine HCl (Medisca NDC 38779-0082-03): 5grams
- Ethoxy Diglycol (Fagron Pharmaceuticals NDC 38779-1903-07): 3mL
- Liquigel (Medisca NDC 38779-2531-01): 3 grams
- Lipoderm Cream Base (PCCA NDC 51927-3338-00): 89 grams

Drug Formula for Vehicle (Per 100gm of cream)

- Lipoderm Cream Base (PCCA NDC 51927-3338-00): 100 grams

Formulation Instructions:

1. Weigh powder reagents in weigh boats and set aside.
2. Tare 100mL unguator jar
3. Place all powders in jar, and top with wetting agent (Ethoxy Diglycol).
4. Mix with a spatula until a thick paste is formed
5. Place emulsifier/thickener (Liquigel) on top of the paste.
6. Pour Lipoderm cream on top (total weight of ingredients should equal 100gm).
7. Using Mixing blade and Unguator e/s, Mix the compound for 2:30 at a mixing speed of 5.

8. Pour contents into jar/pump for patient use.

Labeling:

The formulations will be labeled “For Research Only” and will be coded in order to ensure double-blinding. Blinding will be carried out by random allocation of letters “A” to “E” to label the pharmaceuticals (including the vehicle). This task is carried out at the compounding pharmacy. With delivery of the pharmaceuticals and a list specifying the compounds corresponding to allocated letters is supplied to the PI.

Formation expirations:

As per USP 795 standards on compounding with a water-containing base, these formulations have an expiration of 30 days. The expiration date will be on the label.

Storage:

The formulations will be stored at room temperature in a locked cabinet in the Dermatology lab that only study personnel will have access with a key. Ambient temperature of the storage cabinet will be recorded once a day (except on weekends). Logs of formulation delivery and use per subject will be kept.

Application:

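### The vehicle is plain Lipoderm while every active cream also contains ethoxy diglycol and Liquigel, so each active-versus-vehicle contrast mixes drug with added excipients

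*Combined protocol and SAP*

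**What the plan says.** Section 3 aims at the antipruritic efficacy of the three substances and their combination, and at their mechanism of action. It makes KeAmLi versus vehicle on itch AUC the primary outcome. Section 9 sets all four active creams against vehicle for the secondary outcomes (peak intensity, peak time, duration) and for the exploratory outcomes (thermal and mechanical thresholds, hyperknesis). The post hoc tests in section 10 (Statistical Analysis) follow a Dunnett-like scheme.

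Section 10 names the vehicle only as PCCA Lipoderm. Section 28 agrees and lists a single ingredient per 100 g: "Lipoderm Cream Base (PCCA NDC 51927-3338-00): 100 grams".

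The active formulas in section 28 contain more than drug and base:

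- KeAmLi: "Ethoxy Diglycol (Fagron Pharmaceuticals NDC 38779-1903-07): 5mL", 3 g Liquigel, and "Lipoderm Cream Base (PCCA NDC 51927-3338-00): 72 grams".
- Ketamine: "Ethoxy Diglycol (Fagron Pharmaceuticals NDC 38779-1903-07): 4mL", 3 g Liquigel, 83 g Lipoderm.
- Amitriptyline and lidocaine, each: "Ethoxy Diglycol (Fagron Pharmaceuticals NDC 38779-1903-07): 3mL", "Liquigel (Medisca NDC 38779-2531-01): 3 grams", 89 g Lipoderm.

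The mixing instructions give both ingredients a processing role: "Place all powders in jar, and top with wetting agent (Ethoxy Diglycol") and then "Place emulsifier/thickener (Liquigel) on top of the paste". The documents say nothing about whether either one affects itch or sensation.

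**The concern.** A vehicle control is meant to share everything with the active cream except the drug. Here the two added excipients go in wherever drug goes in and nowhere else. Randomisation, the within-subject comparison, more subjects or a different model cannot pull the two apart, because the confounding is in the product and not in the allocation.

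The objectives concern what the substances do. If ethoxy diglycol or Liquigel changed cowhage itch or a sensory threshold after 30 minutes under occlusion, that change would be reported as drug effect. The imbalance is largest in the primary contrast, because KeAmLi has the most ethoxy diglycol. The protocol does not mention this limit on interpretation.

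**Working it through.** **Inputs.** The formulas per 100 g come from section 28. The 2 g applied per 4 x 4 cm site comes from section 10. The documents give no density for ethoxy diglycol, so 1 mL = 1 g is an assumption, varied below.

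**1. Reproduce the stated batch weight.** Section 28 says the ingredients of a batch total 100 g. Each sum is drug + ethoxy diglycol + Liquigel + Lipoderm:

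- KeAmLi: (10 + 5 + 5) + 5 + 3 + 72 = 100
- Ketamine: 10 + 4 + 3 + 83 = 100
- Amitriptyline: 5 + 3 + 3 + 89 = 100
- Lidocaine: 5 + 3 + 3 + 89 = 100
- Vehicle: 100

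All five reproduce the stated total, so the lists look complete and the vehicle has not lost a line.

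**2. Added excipients.** Parts per 100 = ethoxy diglycol + Liquigel. Grams per site = 2 x parts / 100. Share of the non-drug cream = parts / (100 - drug).

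| Cream | Parts per 100 | Per 2 g site | Share of non-drug cream |
|---|---|---|---|
| KeAmLi | 5 + 3 = 8 | 0.16 g | 8/80 = 10.0% |
| Ketamine | 4 + 3 = 7 | 0.14 g | 7/90 = 7.8% |
| Amitriptyline | 3 + 3 = 6 | 0.12 g | 6/95 = 6.3% |
| Lidocaine | 3 + 3 = 6 | 0.12 g | 6/95 = 6.3% |
| Vehicle | 0 | 0 g | 0% |

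**3. Density range.** At an assumed 0.9 to 1.1 g/mL, KeAmLi carries 4.5 + 3 = 7.5 to 5.5 + 3 = 8.5 parts, or 0.15 to 0.17 g per site. The result does not depend on the density assumption.

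**4. What the contrast estimates.** KeAmLi minus vehicle = drug effect + effect of 5 mL ethoxy diglycol and 3 g Liquigel. For a single-agent cream the second term has 3 or 4 mL and 3 g. To identify that term, some arm would have to carry the excipients without drug. None of the five does.

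**5. What a vehicle matched to KeAmLi would change.** Vehicle of 5 + 3 + 92 = 100; differences are vehicle minus active, per 100 g:

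| Against | Ethoxy diglycol now | Proposed | Liquigel now | Proposed |
|---|---|---|---|---|
| KeAmLi | -5 mL | 0 | -3 g | 0 |
| Ketamine | -4 mL | +1 mL | -3 g | 0 |
| Amitriptyline | -3 mL | +2 mL | -3 g | 0 |
| Lidocaine | -3 mL | +2 mL | -3 g | 0 |

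The Lipoderm gap to KeAmLi falls from 100 - 72 = 28 parts (0.56 g per site) to 92 - 72 = 20 parts (0.40 g). The remaining 20 parts equal the drug powder that displaces base.

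**The case against.** **No effect of the excipients is shown.** True. The documents give them processing roles only, the amounts are 6 to 8 parts per 100, and residual cream is removed before testing. This limits how serious the point can be said to be. It does not make the control matched.

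**The vehicle needs no wetting agent because it holds no powder.** This explains the omission, but what compounding requires does not settle what a control must contain.

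**Lipoderm's own ingredients are not listed.** This stands as a caveat: zero in the vehicle means none added. If the base already contains either ingredient, the relative imbalance is smaller.

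**The single-agent creams act as partial controls.** They carry 6/8 = 75% to 7/8 = 87.5% of KeAmLi's added parts. If excipient effects were proportional to amount and no drug worsened itch, the smallest single-agent effect would roughly bound the bias. This is useful informally, but each of these creams also contains drug. The fraction also depends on which excipient acts: 60% to 80% of the ethoxy diglycol, but 100% of the Liquigel. Moreover, section 9 lists the single-agent contrasts for peak intensity, peak time and duration, not for AUC, and no bounding analysis is planned. The local safety grades record visible reactions only.

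**Hyperknesis is a before-and-after change on the treated site.** A constant excipient effect on touch-evoked itch would largely cancel. That narrows the point for this one outcome, though an excipient effect on the response to cowhage would remain.

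**One vehicle cannot match four creams.** Correct; step 5 of the working shows the remaining 1 to 2 mL mismatch. The primary contrast can still be matched on both excipients.

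**Conclusion.** The point holds. As written, every active-versus-vehicle contrast, including the primary one, compares drug plus ethoxy diglycol plus Liquigel with plain Lipoderm. The imbalance is 8 parts per 100 in the primary contrast, about 0.16 g per 2 g site (0.15 to 0.17 g at 0.9 to 1.1 g/mL), and 6 to 7 parts in the others. These are amounts applied; what stays in the skin after wiping is unknown.

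Confidence is high on what the contrasts estimate, because the formulas settle it. Nothing in the documents allows the effect on AUC or thresholds to be sized or even signed, so this is a possible bias and not a demonstrated one. It does not touch sample size, power or alpha. It should be fixed because it reaches the primary endpoint, cannot be repaired by analysis afterwards, and is cheap to remove beforehand.

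**What to change.** Before the first subject, change the vehicle formula in section 28 to 5 mL ethoxy diglycol, 3 g Liquigel and Lipoderm to 100 g (about 92 g), and describe the vehicle accordingly in section 10. This matches both added excipients in the primary contrast and Liquigel in all five creams. State the remaining ethoxy diglycol excess of 1, 2 and 2 mL per 100 g over the ketamine, amitriptyline and lidocaine creams, and that the remaining base difference is displaced drug powder.

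The pharmacy should first confirm that the mixture makes a usable cream, since the written mixing steps start from a powder paste that the vehicle would not have.

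The cost is one changed formula with the same pharmacy and ingredients, and possibly a formulation update to the IND. No subjects or visits are added. The creams expire after 30 days and enrolment lasts 6 months, so the vehicle must be compounded about 6 to 7 times anyway (182/30 = 6.1). A switch after enrolment begins would mix two vehicles, so the change should come first.

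If the vehicle is not changed, add one sentence to section 9 and to Statistical Analysis saying that active-versus-vehicle contrasts estimate the effect of the full formulation (drug, ethoxy diglycol and Liquigel in Lipoderm) against Lipoderm base. That makes the interpretation accurate but leaves the confounding in place.
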